## BACKGROUND INFORMATION

Since 1978, influenza A (H1N1) influenza A (H3N2) and influenza B virus are commonly circulating every season. Then, the trivalent influenza vaccine had been developed against the three kinds of influenza virus (H1N1 and H3N2 and B). According to the result of global influenza surveillance, the World Health Organization has been to predict the next season's pandemic strains for more than 30 years. WHO recommended vaccine components containing two subtypes of A influenza virus (H1N1 and H3N2) and a subtype of B influenza virus (B/Victoria lineage or B/Yamagata lineage). However, since the 2001-2002 influenza season, two strains of influenza B have been circulating together. This made it difficult to predict the dominant strain of influenza B in the next influenza season. Several studies demonstrated that in 7 of the past 13 seasons, major circulating subtype of B virus strains was not included in the vaccine, which significantly reduces the immunological effects of the influenza vaccine. Unincluded subtype B influenza virus caused a potential threat to human beings. To expand the broad protection of the seasonal influenza vaccine and improve the protective effect of the vaccine, many influenza vaccine manufacturers had actively carried out the development of the quadrivalent influenza vaccine, which has become an important direction for the upgrading of influenza vaccine.

At the same time, several studies showed that the influenza vaccine induces a poor immune response in young children. Unvaccinated children below 3 years old were induced by vaccine weaker than unvaccinated children above 3 years old younger or vaccinated children below 3 years old, especially for the B subtype influenza virus. For 6 ~ 35 months old children were recommended vaccination dosage of 0.25 ml antigen of influenza inactivated vaccines. This recommendation was based on the observation in the 1970s of increased adverse reactivity in younger children with an adult's dosage of whole-virus inactivated influenza vaccines, especially the fever. but at present in the seasonal flu vaccine has been without the use of an inactivated virus. The safety and immunogenicity of 0.5ml and 0.25ml dosage antigen of vaccine were evaluated in 6~35 months children in a large number of clinical trials. The results showed that the high dosage of the split vaccine was well tolerated and could induce a strong immune response. Hence, in 2016, the FDA approved the adult dosage of the influenza vaccine for children above 6 months. Besides, many countries such as Canada, Brazil, Mexico, Finland, and Britain approved dosage of 15µg and

7.5 µg antigen for children below 3 years.

Given the situation of children-using the influenza vaccine, we carried out the clinical trial of the quadrivalent influenza vaccine suitable for children aged 6 to 35 months, which is of great significance for children to prevent influenza in China.

## STUDY OBJECT

To evaluate the immunogenicity and safety of 2 doses of quadrivalent influenza virus split vaccine (0.25ml/ dose and 0.5ml/ dose) in healthy population aged 6-35 month., so as to provide a data support for phase III clinical trials.

## STUDY DESIGN

A randomized, double-blind, parallel control design was set to enroll 1,980 healthy subjects aged 6-35 months. Subjects were randomly inoculated with experimental vaccine 1, experimental vaccine 2, control vaccine 1 or control vaccine 2 in a ratio of 2:2:1:1 for safety and immunogenicity evaluation. The inoculation time was 0 and 28 days.

### Immunogenicity observation

- All subjects were required to take bloody samples for 2 times, each time about 3.0ml, for the detection of influenza virus HI antibody:
- First time: before the first dose;
- Second dose: 28 (+10) days after the second dose.
- After 30 days of safety observation and 28 days of immunogenicity test results after 2 doses of immunization, uncovered blind and the immunogenicity results were statistically analyzed.

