## STUDY ENDPOINT

### Immunogenicity

(1) 28 days after receiving two doses of vaccine in subjects aged 6-35 months, seroconversion rate of HI antibodies against any subtype of influenza virus in each group.

(2) 28 days after receiving two doses of vaccine in subjects aged 6-35 months, seroprotection rate of HI antibodies against any subtype of influenza virus in each group.

(3) 28 days after receiving two doses of vaccine in subjects aged 6-35 months, GMT and GMI of HI antibodies against any subtype of influenza virus in each group.

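### Do the two descriptions of the second serum window, one counted from dose 2 and one given as day 56 (+10), conflict in a way that affects the immunogenicity results?

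*Combined protocol and SAP*

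**What the plan says.** All places are in the combined protocol and SAP.

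- **Study design** gives the vaccination schedule without a window: "The inoculation time was 0 and 28 days".
- **Immunogenicity observation** sets the second blood sample at "28 (+10) days after the second dose".
- **Safety observation, group table** lists inoculation at day 0 and day 28 (+10), and serum collection at day 0 and day 56 (+10). Both columns are headed in days. Neither says whether the later entries are fixed days from dose 1 or nominal days that move with the actual second dose.
- **Study endpoint, Immunogenicity** times seroconversion, seroprotection, GMT and GMI at "28 days after receiving two doses of vaccine in subjects aged 6-35 months", so the endpoints also count from completion of the two doses.
- **Data statistics, immunogenicity** compares rates between groups and sets the results against 40% seroconversion, 70% seroprotection and a 2.5-fold GMI. It defines no per-protocol set and has no rule for samples drawn outside a window.

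**The concern.** Each serum column entry starts at 0, so a reader may take day 56 (+10) as a hard range of days 56 to 66 from dose 1. The same table lets dose 2 slip to day 38, and the sampling instruction counts its 28 (+10) days from that dose. On this reading one sample can be in window in one place and out in the other:

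- Dose 2 on day 35 and blood on day 68 is 33 days after dose 2. That meets the instruction but is two days past the table's limit.
- Dose 2 on day 38 and blood on day 56 meets the table but is only 18 days after dose 2, ten days short of the instruction and of the endpoint's time point.

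The second draw is the only one after baseline, and every immunogenicity result rests on it. If the choice of window decided which samples counted, or led sites to bleed early, the results set against 40%, 70% and 2.5-fold could shift, and the early samples would not measure the stated endpoint.

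**Working it through.** **Inputs.** Dose 2 on study days 28 to 38 (group table). Serum by the text: 28 to 38 days after dose 2 (Immunogenicity observation). Serum by the table: days 56 to 66, read literally from dose 1 (group table).

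**Step 1: reproduce the table's figure.** With dose 2 on day 28, the text gives 28 + 28 = 56 to 28 + 38 = 66. This is exactly day 56 (+10), so the nominal arithmetic is right.

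**Step 2: let dose 2 slip.** For dose 2 on day *d*, the text window is *d* + 28 to *d* + 38. Read as days since dose 2, the table window is 56 − *d* to 66 − *d*.

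| Dose 2 day | Text window (study day) | Table window (study day) | Shared days | Table window in days after dose 2 |
|---|---|---|---|---|
| 28 | 56–66 | 56–66 | 11 | 28–38 |
| 30 | 58–68 | 56–66 | 9 | 26–36 |
| 33 | 61–71 | 56–66 | 6 | 23–33 |
| 35 | 63–73 | 56–66 | 4 | 21–31 |
| 38 | 66–76 | 56–66 | 1 | 18–28 |

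The number of shared days is 66 − (*d* + 28) + 1 = 39 − *d*, which runs from 11 down to 1 and never reaches 0. A single draw can therefore always satisfy both statements.

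**Step 3: count the combinations.** There are 11 dose 2 days and 11 sample days in each window, so each window allows 11 × 11 = 121 pairs.

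- Pairs meeting both: 11 + 10 + … + 1 = 66.
- Pairs meeting the text only (study days 67 to 76): 121 − 66 = 55, or 45%.
- Pairs meeting the table only (18 to 27 days after dose 2): 121 − 66 = 55, or 45%.

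**Step 4: see how far the 45% depends on assumed delays.** Let *x* be the delay of dose 2 past day 28 and *y* the delay of the draw past 28 days after dose 2. The draw falls after day 66 when *x* + *y* > 10.

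- Both delays 0 to 10 days: 55 of 121 pairs (45%).
- Both delays 0 to 7 days: 4 + 3 + 2 + 1 = 10 of 64 pairs (16%).
- Both delays 0 to 5 days: the largest sum is 10, so none.

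These count combinations on an even grid. They are not expected proportions of children, and the document gives no distribution of visit dates with which to choose among them.

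**Step 5: trace the route to the results.** A divergence matters only if it changes who is analysed or when blood is drawn.

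- *Who is analysed.* Nothing in the statistical section drops a sample for its date, so calling it late by one window and on time by the other changes no analysis set.
- *When blood is drawn.* A draw at 18 to 27 days requires staff to take the table cell as overriding the explicit instruction to count from dose 2. Staff who follow the instruction, or both statements together, draw at 28 to 38 days.

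**The case for a change.** The best case for a change is that the literal reading of the table is a natural one. Both columns start at 0, and no sentence says that day 56 moves with the second dose. The statistical section defines neither an evaluable sample nor a treatment of out-of-window draws, so whether a given draw is a deviation would be settled after the fact. The one post-baseline sample carries every immunogenicity result, and the repair would be one table cell and one sentence, with no extra visit.

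Part of this stands. The anchor is unstated, the literal reading does diverge by up to ten days when dose 2 is late, and the worked examples are correct.

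It does not carry the conclusion, for three reasons. First, the two statements are not incompatible: they coincide at the nominal schedule and overlap on every permitted dose 2 day. Since 56 is 28 + 28 and carries the same (+10), the ordinary reading is a nominal timetable, under which there is no conflict. Second, the missing rule on out-of-window samples weakens the argument, because without such a rule the mismatch cannot move a sample in or out of the analysis. Whether a rule is needed is a separate question. Third, the proposed anchor is already the one used by the sampling instruction and the endpoint definitions, so the edit would restate the plan. The schedule is also common to all four groups, and no differential effect on the between-group comparisons has been shown. At most the absolute thresholds could be touched, by an amount nobody can state.

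**Conclusion.** The concern does not call for a change to the plan. The day counts are correct: read literally from dose 1, the table covers days 56 to 66 while the text reaches day 76, and the table would allow draws as early as 18 days after dose 2. But the two windows agree when dose 2 is on day 28 and always share at least one day. Two parts of the plan already tie the sample to the second dose, and an analyst or site would sensibly read day 56 as 28 + 28. This is an unlabelled anchor in a summary table, not an arithmetic error, and clarifying it would change no result that can be shown.

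This rests on two assumptions: that sites schedule the draw by the sampling instruction, and that no rule outside this document excludes samples by study day. The share of draws on which the windows disagree runs from 0% to 45% purely according to the delays assumed, so it cannot support a statement about the size of any effect.

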## STUDY ENDPOINT

### Immunogenicity

(1) 28 days after receiving two doses of vaccine in subjects aged 6-35 months, seroconversion rate of HI antibodies against any subtype of influenza virus in each group.

(2) 28 days after receiving two doses of vaccine in subjects aged 6-35 months, seroprotection rate of HI antibodies against any subtype of influenza virus in each group.

(3) 28 days after receiving two doses of vaccine in subjects aged 6-35 months, GMT and GMI of HI antibodies against any subtype of influenza virus in each group.

### Safety

(1) The proportion of all adverse reactions/events in each group through 30 days after the second dose.

(2) The proportion of serious adverse events (SAE) within 6 months after inoculation in each group.

## SAFETY OBSERVATION

Systemic adverse reactions: Fever, Diarrhea, constipation, difficulty swallowing, anorexia, vomiting, nausea, muscle pain (not the vaccination site), arthritis, joint pain, headache, new convulsions, cough and difficulty breathing, the vaccination site itching (no skin damage), abnormal skin and mucosa, insomnia, irritability, or inhibiting, acute allergic reaction to pain, fatigue, lack of power, not the vaccination site.

Local adverse reactions: pain, induration, swelling, rash, redness, itching

## **IMMUNOGENICITY OBSERVATION**

Seroconversion: 1:10 is the lowest serum dilution. Prevacination HI titer < 1:10 and postvaccination titer  $\geq$  1:40 or a prevaccination titer  $\geq$  1:10 and at least a 4-fold increase in the postvaccination titer

Seroprotection: Postvaccination titer  $\geq$  1:40 is considered to have antibody protection.

GMT: geometric mean titer.

GMI: GMT increase fold.

## **EVALUATION CRITERIA OF SAFETY**

The safety evaluation of each group will be divided into three stages. From the first dose inoculation to day 7 after inoculation; From the first dose inoculation to day 21 after inoculation; From the second dose inoculation to day 30 after the second dose inoculation. The first stage is the basis for the follow-up group of the same vaccine, and will be carried out under blind. The latter two stages are the basis for evaluation of vaccine safety, and will be carried out under unblind. If each evaluation is not found level 4 local and systemic adverse reactions associated with vaccine and the total incidence rate of level 3 of local and systemic adverse reactions and abnormal laboratory test which associated with the vaccination is lower than 15%, that the vaccine will be acceptable safety.

## **EVALUATION CRITERIA OF IMMUNOGENICITY**

If seroconversion rate is higher than 40%, the antibody protection rate higher than 70%, GMI more than 2.5 times, the vaccine will be acceptable immunogenicity.

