## DATA STATISTICS

### Statistics analysis of immunogenicity

The prevaccination and postvaccination geometric mean of antibody and its 95% confidence interval (confidence interval, CI) will be described. The postvaccination serum conversion rate and protection rate of antibody and their 95% CI will be described.

Comparisons will be conducted to evaluate differences in response between study groups using a  $\chi^2$  test or Fisher's exact test to compare to the difference of serum conversion rate and protection rate. Statistical significance will be considered at a level of  $\alpha = 0.05$  and all tests will be 2-sided.

If serum HI antibody conversion rate is more than 40%; protection rate more than 70%; GMI more than 2.5 folds, the immunogenicity will reach the design requirements.

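### Must the immunogenicity acceptance rule state how many strains must pass, which group is judged, and a confidence interval for GMI?

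*Combined protocol and SAP*

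**What the plan says.** The acceptance rule appears twice in the combined protocol and SAP. EVALUATION CRITERIA OF IMMUNOGENICITY reads "If seroconversion rate is higher than 40%, the antibody protection rate higher than 70%, GMI more than 2.5 times", and concludes that "the vaccine will be acceptable immunogenicity". Statistics analysis of immunogenicity repeats the thresholds: "If serum HI antibody conversion rate is more than 40%; protection rate more than 70%; GMI more than 2.5 folds". Neither place names a strain, a number of strains, a group, or the type of estimate.

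STUDY ENDPOINT (Immunogenicity) supplies part of what is missing. Its third item is "GMT and GMI of HI antibodies against any subtype of influenza virus in each group", and the seroconversion and seroprotection items use the same form, all at 28 days after two doses.

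Two sets of intervals are planned: "The prevaccination and postvaccination geometric mean of antibody and its 95% confidence interval", and for the rates, "The postvaccination serum conversion rate and protection rate of antibody and their 95% CI will be described". GMI has none. On timing, Immunogenicity observation says that after the 30-day safety period and the antibody results, "uncovered blind and the immunogenicity results were statistically analyzed".

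**The concern.** The product has four strains and the trial has two experimental vaccines, yet the rule speaks of one vaccine and one set of values. If one strain misses a threshold, the same data can be called acceptable or not, depending on a count that is not written down. The analysis follows unblinding, so that count could be chosen with the group results in view. The trial is meant to support phase III, and this is its only immunogenicity rule with a threshold.

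Three smaller points add to the impression:

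- No conjunction joins the three criteria.
- The safety criteria do name a unit: "The safety evaluation of each group will be divided into three stages".
- GMI decides acceptance but is the only one of the three measures without a planned interval. That interval cannot be rebuilt from the intervals for the pre and post means, because the fold rise is paired within child.

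**Working it through.** **Inputs.** The thresholds are 40%, 70% and 2.5, from the two sections above. There are four strains (STUDY OBJECT: quadrivalent). For Experimental Vaccine 2, the 2:2:1:1 ratio in STUDY DESIGN gives 1,980 × 2/6 = 660 children, but the table under Safety observation gives 330. Both sizes are used below. The plan states no expected response, SD or power for this rule, so there is no figure to reproduce. All true values below are assumed.

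**Step 1. What the text settles.** The three quantities in the rule are the three endpoint measures, and those are defined by subtype and in each group. Reading the rule per strain and per group therefore needs only a cross-reference. Three thresholds after a single *if* read naturally as joint. The contrast with safety is weak: that section uses each group to introduce its stages, and its verdict is again about the vaccine. Two items stay open: the number of strains that must pass (k), and point estimate or lower limit.

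**Step 2. What k does.** For a rate, the pass probability is P(X/n > threshold) with X binomial. For GMI, the mean log2 fold rise is taken as normal with SE = SD/√n and SD 2.0. At true values of 72%/42%/2.7 (seroprotection, seroconversion, GMI), one strain meets all three criteria, if they are independent, with probability

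- n=330: 0.774 × 0.751 × 0.843 = 0.490, so 4 of 4 gives 0.490⁴ = 0.058;
- n=660: 0.864 × 0.842 × 0.923 = 0.671, so 4 of 4 gives 0.671⁴ = 0.203.

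The measures come from the same children's titres, so independence is implausible. The table assumes a correlation of 0.5 between strains and between criteria (Gaussian copula), with the independent 4-of-4 result for comparison.

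| All four strains truly | n | At least 1 | At least 3 | 4 of 4 | 4 of 4, independent |
|---|---|---|---|---|---|
| 72%/42%/2.7 | 330 | 88% | 51% | 27% | 6% |
| 72%/42%/2.7 | 660 | 95% | 69% | 44% | 20% |
| 75%/45%/3.0 | 330 | 99.7% | 95% | 83% | 76% |
| 75%/45%/3.0 | 660 | 100% | 99.7% | 97% | 97% |

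Next, take three strains at 80%/55%/4.0 and a fourth at 45% seroconversion and GMI 3.0. The rules requiring at least one strain or 3 of 4 accept in over 99.9% of trials. The 4-of-4 rule depends on the fourth strain's true seroprotection:

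| Fourth strain | n=330 | n=660 |
|---|---|---|
| 65% | 2% | 0.3% |
| 70% | 46–48% | 48–49% |
| 75% | 93–94% | 99% |

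So k decides the verdict when a strain is near or below a threshold, and seldom matters otherwise.

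**Step 3. Point estimate or lower limit.** At a true seroprotection of 70%, one strain passes on the point estimate with probability 0.479 (n=330) or 0.485 (n=660). A Clopper-Pearson lower 95% limit above 70% needs 248/330 (75.2%) or 486/660 (73.6%), and the pass probability is 0.022. The choice matters. The literal reading is the point estimate, since the rule compares the rate itself, and the planned intervals for both rates let a reader apply the stricter test.

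**Step 4. The GMI interval.** The 95% limits are GMI divided and multiplied by 2^(1.96 × SD/√n). For an observed 2.7:

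| SD of log2 fold rise | n=330 | n=660 |
|---|---|---|
| 1.0 | 2.505–2.91 | 2.56–2.85 |
| 1.5 | 2.41–3.02 | 2.49–2.92 |
| 2.5 | 2.24–3.26 | 2.37–3.08 |

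Whether 2.5 lies inside depends on an SD that the documents do not give: it does at 1.5 and 2.5, and does not at 1.0. In every row the point estimate passes, so the interval alters no verdict reached on it. It is true that the two planned GMT intervals cannot replace it. Treated as unpaired, they overstate the log-scale width by 1/√(1−r), which is 1.20-fold at a pre/post correlation of 0.3 and 1.41-fold at 0.5 (equal SDs). But the paired titres are collected, so the interval can be computed whenever it is wanted.

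**The case for a change.** The strongest case for a change comes from the plan's own background. The quadrivalent product exists to add the second B lineage, and the background says young children respond poorly, above all to B strains. One weak B strain is therefore the failure that the documents themselves anticipate, and it is the case in which k settles the answer. The wording *any subtype* in the endpoints can mean each or at least one, and even when read as each it fixes no count. Writing k down before unblinding would cost a sentence.

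Much of this stands. The count is not stated, and a one-word verdict chosen after unblinding would carry little weight. But the remedy would have to leave k blank for the sponsor, because nothing in the documents determines it. A rule of 4 of 4 often rejects a vaccine whose strains all sit about 2 points above the rate thresholds, while 3 of 4 accepts one whose fourth strain fails. Nor would fixing k remove sampling error at a threshold. The protection against a convenient choice is the report by strain and group that the endpoints already call for: a strain below 40%, 70% or 2.5 is visible there under any k.

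**Conclusion.** No change to the plan follows. The rule is terse, but no stated rule or calculation is shown to give a wrong result. Group and strain follow from the endpoint definitions, and the joint reading of the three criteria is the natural one. The number of strains and the type of estimate remain open, and they can matter: with one strain at 65% seroprotection, acceptance runs from over 99.9% (3 of 4) to 2% or less (4 of 4). That spread measures a trade-off between two defensible rules, and it shrinks when all strains are clear of the thresholds (95% against 83% at 75%/45%/3.0, n=330, correlation 0.5). The GMI interval is useful reporting, but it leaves a point-estimate verdict as it is.

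This conclusion rests on two things: that results are reported for each of the four strains in each experimental group, as the endpoints imply, and that all true rates, correlations and SDs used here are assumptions, since the documents give none.

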## **STUDY STATUS**

Record Verification: January 2020

Study Start: April 2020

Primary Completion: August 2020

Study Completion: March 2021

## **ELIGIBILITY**

Inclusion Criteria

Healthy infants aged 6-35 months.

Volunteer legal guardian or client informed consent, voluntarily participate in and sign informed consent.

The volunteer legal guardian or client has the ability (non-illiterate) to understand the study procedures, to use a thermometer, scale, and fill in a diary card as required, and be able to complete the clinical study in compliance with the clinical trial protocol.

